#### 8. SELECTION OF STUDY POPULATION

The study will enroll a sufficient number of subjects to ensure that at least 48 subjects complete the study (24 subjects per group with at least 16 females in total). Replacement subjects may be added at the discretion of the sponsor with the agreement of the Investigator(s).

#### 8.1. Inclusion Criteria

Subjects must meet each one of the following inclusion criteria in order to be eligible for participation in the study:

- 1. Subject must provide written informed consent prior to the conduct of any study-related procedures.
- 2. Male or female, 18-55 years of age, inclusive.
- 3. Subjects with a diagnosis of moderate or severe opioid use disorder (DSM-V) who are currently physically dependent on IV or insufflated opioids, and who are willing to undergo short-term BPN treatment.
- 4. Self-reported opioid-use of a minimum of 21 days in the 30 days prior to Screening.
- 5. Positive UDS for opioids at Screening or at check-in. If UDS is not positive, subjects must present with physical signs of withdrawal, as determined by the Investigator. The Investigator may administer a naloxone challenge, in order to confirm opioid dependence at the Investigator's discretion.
- 6. Female subjects of childbearing potential must be willing to use a reliable method of contraception during the entire study (Screening Visit to Follow-Up phone call), as defined in Section 10.1.6.
- 7. Female subjects of non-childbearing potential should be surgically sterile (i.e., have undergone complete hysterectomy, bilateral oophorectomy, or tubal ligation) or in a menopausal state (at least 1 year without menses), as confirmed by follicle stimulating hormone (FSH) levels.
- 8. Male subjects with female partners of childbearing potential must agree to use a reliable method of contraception from Screening Visit through at least 3 months after the last dose of study drug. Male subjects must also agree not to donate sperm during the study through at least 3 months after the last dose of study drug.
- 9. Is willing and able to comply with the study requirements (including blood sampling), complete study assessments, visit the clinic and remain confined in the CRU for up to 25 consecutive days.

Version: 2.0, 17NOV2015 Page 44 of 99

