
<sup>b Prior to enrollment in the Qualification Phase of this study, all Inclusion and Exclusion criteria must be met.

<sup>o Brief update on the subject's medical and medication history since Screening at inpatient check-in only.

<sup>d A complete physical exam of all major body systems will be performed during Screening including height, weight and BMI.

<sup>e Abbreviated (symptom-directed) physical examination performed at the investigator's discretion (height will not be measured)

f ECGs performed prior to dosing with CAM2038 q1w

g Urine drug screen will be administered at Screening and inpatient check-in. Additional urine drug screens may be performed at the investigator's discretion.

	Screening	Inpatie	Inpatient Qualification Phase			Inpatient Treatment Phase				
Visit:	1				2					
Day:	-39 to -11	-10, -9, -8, -7, OR -6	-9, -8, -7, -6, OR -5 to -4	-3 to -1	0	1 to 3 & 4 to 6	7	8 to 10 & 11 to 13	14/ ET	21
Pregnancy Test	X h	X h		Xi	Xi		Xi			
FSH Test j	X									
Laboratory Tests k	X	X							X	
Pulse Oximetry/Cardiac monitoring/Respiratory Rate Monitoring		X 	X	X m	X	X m	X	X m		
Vital Signs n	X	X	X	X°	Xp	X°	X p	X°	X	

h A serum pregnancy test will be performed for all females of childbearing potential during Screening and at inpatient check-in. Following inpatient check-in and throughout the duration of confinement, urine pregnancy tests may be administered at the Investigator's discretion.

Version: 2.0, 17NOV2015 Page 38 of 99

A urine pregnancy test will be performed for all females of child-bearing potential only prior to IM hydromorphone injection on Day -3 and prior to dosing with CAM2038 q1w on Day 0 and Day 7.

<sup>j If post-menopausal females do not have a record of a FSH test, post-menopausal females will have a FSH test at Screening.

<sup>k Includes chemistry, hematology, urinalysis and coagulation profile.

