## **10.1.6.** Contraceptive Requirements

Female subjects of childbearing potential must be using and willing to continue using medically acceptable contraception during the study. Examples of medically acceptable forms of contraception include true abstinence, hormonal contraceptives (combined oral pill, patch or vaginal ring, intrauterine device or system, progestin implant or injection), bilateral tubal ligation, or double-barrier methods (e.g., male condom with spermicide in addition to a diaphragm or a contraceptive sponge).

Female subjects of non-childbearing potential are not required to use contraception and to undergo pregnancy tests; however, they must have documentation supporting that they are surgically sterile (hysterectomy and/or bilateral oophorectomy/salpingo-oophorectomy, as determined by subject medical history) or congenitally sterile, or must be post-menopausal. Post-menopausal is defined as being amenorrheic for at least 2 years without another cause or amenorrheic for at least 1 year without another cause and a documented FSH level ≥50 mIU/mL.

Male subjects with female partners of childbearing potential must agree to use a medically acceptable method of contraception from Screening Visit through at least 3 months after the last dose of study drug. Male subjects must also agree not to donate sperm during the study through at least 3 months after the last dose of study drug.

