# 10.2. Eligibility Review

Prior to receiving the first dose of hydromorphone on Day -3, subjects must meet all inclusion and not meet any exclusion criteria as outlined in Sections 8.1 and 8.2.

The Investigator or designee must document that the subjects meet each individual criterion via a signed note or eligibility and clinical stability checklist during Screening. Signatures on these documents must be dated on or before the date of Day -10.

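### Inclusion 7 classes tubal ligation as sterility while Section 10.1.6 treats it as contraception, so a site could schedule no required pregnancy tests for a woman who should have up to 5

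*Protocol*

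**What the plan says.** All references are to the Protocol.

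- **Inclusion 7 (Section 8.1 and synopsis).** "Female subjects of non-childbearing potential should be surgically sterile (i.e., have undergone complete hysterectomy, bilateral oophorectomy, or tubal ligation". The other route to this class is menopause, confirmed by FSH. The item does not refer to Section 10.1.6. Inclusion 6 in Section 8.1, which covers women of childbearing potential, does.
- **Section 10.1.6, first paragraph.** The examples of acceptable contraception for women of childbearing potential include "progestin implant or injection), bilateral tubal ligation, or double-barrier methods".
- **Section 10.1.6, second paragraph.** "Female subjects of non-childbearing potential are not required to use contraception and to undergo pregnancy tests". The sentence then sets a condition: "they must have documentation supporting that they are surgically sterile (hysterectomy and/or bilateral oophorectomy/salpingo-oophorectomy, as determined by subject medical history". Congenital sterility and post-menopausal status also qualify. Tubal ligation does not appear.
- **Table 4, footnote h.** "A serum pregnancy test will be performed for all females of childbearing potential during Screening and at inpatient check-in". Later urine tests during confinement are allowed at the investigator's discretion.
- **Table 4, footnote i.** "A urine pregnancy test will be performed for all females of child-bearing potential only prior to IM hydromorphone injection on Day -3", and again before the depot injections on Day 0 and Day 7.
- **Section 10.2.** The person who confirms eligibility against Sections 8.1 and 8.2 "must document that the subjects meet each individual criterion via a signed note or eligibility and clinical stability checklist during Screening".
- **Section 10.4.3.** The serum tests follow the visits in Table 4. Urine tests precede the Qualification challenge and the Day 0 and Day 7 depot injections. Serum results must be negative before the subject continues or is dosed. The childbearing limit is not restated here.

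**The concern.** A woman whose only relevant history is tubal ligation belongs to one class under the eligibility criterion and to the opposite class under the contraception section. No sentence says which definition governs. The class matters because the required pregnancy tests depend on it.

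Those tests are the scheduled laboratory check behind the pregnancy part of exclusion 11. They come before hydromorphone doses of up to 18 mg and before two week-long buprenorphine depot injections. In a multi-site study, two sites could each follow the protocol's own words and check the same woman differently before dosing.

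**Working it through.** The documents state no total number of pregnancy tests, so there is no figure to reproduce. The check compares the two classifications and counts the scheduled tests.

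**Step 1. Classification of a woman whose only ground is tubal ligation**

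| Source | Treatment of tubal ligation | Class |
|---|---|---|
| Inclusion 7 (8.1, synopsis) | A form of surgical sterility | Non-childbearing |
| 10.1.6, contraception list | A method used by women of childbearing potential | Childbearing |
| 10.1.6, sterility list | Not listed | Does not qualify as non-childbearing |

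**Step 2. Required tests if she is of childbearing potential**

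- Footnote h: Screening + check-in = 2 serum tests.
- Footnote i: Day -3 + Day 0 + Day 7 = 3 urine tests.
- Total for a woman who reaches the Day 7 injection: 2 + 3 = 5.
- Total if she stops after Qualification: 2 + 1 = 3, because the Day 0 and Day 7 tests are tied to depot dosing.
- Total if she receives the Day 0 injection but stops before Day 7: 2 + 2 = 4.

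**Step 3. Required tests if she is of non-childbearing potential**

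Footnotes h and i do not reach her, so the count is 0. This zero follows from the scope of the footnotes; neither footnote states an exemption for her.

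**Step 4. Which reading the text supports better**

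The only sentence that exempts anyone from pregnancy tests is in Section 10.1.6, and tubal ligation alone does not meet its conditions. On the text as a whole, up to 5 tests is the better-supported reading.

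A site can still arrive at 0. Section 10.2 directs it to sign off the criteria in Sections 8.1 and 8.2, and inclusion 7 tells it that she is non-childbearing without sending it to Section 10.1.6. It may then apply footnotes h and i directly.

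**Step 5. Study-wide size**

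The documents do not say how many women would be affected, and it could be none. For k affected women, the most extra required tests is 5k. With k assumed to be 0, 1 or 4, that is 0, 5 or 20.

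**The case against.** The strongest reply is that the protocol already settles the matter in favour of testing. The opening of Section 10 says that assessments follow Table 4 and that the sections below it give the details. Section 7.1.5 also points to Section 10 for procedures. Section 10.1.6 therefore governs, its exemption does not cover tubal ligation, and Section 10.4.3 describes the tests without any childbearing limit.

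Much of this stands, and it is why zero is the weaker reading. It does not remove the conflict. None of these places changes the class that inclusion 7 assigns. Section 10.4.3 defers to Table 4 for the serum tests, and the footnotes to Table 4 bring the childbearing limit back.

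A second reply is that little turns on it. Both readings accept tubal ligation as pregnancy prevention, she can enter under inclusion 6 or inclusion 7, and discretionary urine tests remain available. This also stands, and it limits the weight of the point. Discretionary tests are optional and begin only after check-in, so they do not replace the required ones.

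A reader might infer that Table 4 itself offers two equally valid schedules, 0 or 5. The documents do not support that. The footnotes name no exempt group, and the one explicit exemption excludes her. Nor does every affected woman stand to miss 5 tests, since the count depends on how far she gets in the study.

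**Conclusion.** The text is wrong as written: it is an internal inconsistency in the current protocol. Inclusion 7 and Section 10.1.6 define surgical sterility differently, and the required pregnancy testing depends on which definition a site uses. A site relying on inclusion 7 could schedule no required tests, where the better-supported reading requires up to 5.

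The conclusion assumes that tubal ligation is the woman's only ground for the non-childbearing class. A woman who has also had a hysterectomy, or who is post-menopausal, is not affected.

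This is a minor safety-consistency correction. It would be too strong to infer that ineligible women would enter or that the results are at risk. Eligibility is the same under either reading, and the power calculation and the analysis of Drug Liking do not depend on childbearing class.

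**What to change.** 1. In inclusion 7, in both Section 8.1 and the synopsis, delete *or tubal ligation* and refer to Section 10.1.6 for the definition of surgical sterility only.
2. Add to Section 10.1.6: *Women with tubal ligation are of childbearing potential using an accepted method and have all scheduled pregnancy tests.*

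The correction runs in this direction because Section 10.1.6 holds the only exemption from testing and does not grant it for tubal ligation.

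The cross-reference should be confined to surgical sterility. Inclusion 7 asks for FSH confirmation of menopause, and footnote j adds that, where no FSH record exists, "post-menopausal females will have a FSH test at Screening". Section 10.1.6 asks for an FSH value (at least 50 mIU/mL) only on its 1-year amenorrhoea route, not on the 2-year route. Changing those rules could reclassify other women and is not part of this correction.

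The cost is protocol wording plus at most 5 tests (2 serum, 3 urine) per affected woman, all of kinds already in the schedule. No existing test is removed.

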#### 8.2. Exclusion Criteria

Subjects will not be eligible to participate in this study if any one of the following exclusion criteria is met:

- 1. History or presence of any clinically significant psychiatric, endocrine, hematologic, hepatic, immunologic, metabolic, urologic, pulmonary, neurologic, dermatologic, renal, or other major disease or illness at Screening, which in the opinion of the Investigator would jeopardize the safety of the subject or the validity of the study results.
- 2. Opioid dependent subjects who are actively seeking treatment for their moderate to severe opioid use disorder.
- 3. Subjects with positive urine drug screens for buprenorphine, alcohol, barbiturates, or methadone or breath alcohol on the day of check in to the CRU.
- 4. Aspartate aminotransferase levels >3 X the upper limit of normal, alanine aminotransferase levels >3 X the upper limit of normal, total bilirubin >1.5 X the upper limit of normal, or creatinine >1.5 X upper limit of normal on the Screening laboratory assessments and at inpatient check-in, or other clinically significant laboratory abnormalities, which in the opinion of the Investigator may prevent the subject from safely participating in study.
- 5. Any clinically significant abnormality on the basis of medical history, vital signs, physical examination, 12-lead electrocardiogram (QTcF ≥450 msec. for males or ≥470 msec. for females), and laboratory evaluation (including hematology, clinical chemistry, urinalysis, and serology [optional]) at Screening, in the opinion of the Investigator.
- 6. Significant symptoms, medical conditions, or other circumstances which, in the opinion of the Investigator, would preclude compliance with the protocol, adequate cooperation in the study or obtaining informed consent, or may prevent the subject from safely participating in study (including, but not limited to, the risks described as precautions, warnings, and contraindications in the current version of the Investigator's Brochure for CAM2038).
- 7. Subjects will be carefully screened to exclude individuals presenting with a clinically significant history of seizure disorders, history of asthma or other respiratory disorders, head injury, hypertension or personal history of cardiovascular disease or clinically significant ECG abnormalities.
- 8. Current diagnosis of Acquired Immune Deficiency Syndrome (AIDS).
- 9. Current diagnosis of chronic pain requiring opioids for treatment.
- 10. Subjects who currently meet the criteria for a diagnosis of moderate or severe substance use disorder according to DSM-V criteria for any other substances other than opioids, caffeine or tobacco.
- 11. Pregnant or lactating, or planning to become pregnant during the study.
- 12. Clinically significant history of or current evidence of suicidal ideation or active suicidal behavior as based on the Columbia-Suicide Severity Rating Scale (C-SSRS; grade 4 or 5).

Version: 2.0, 17NOV2015 Page 45 of 99

- 13. Hypersensitivity or allergy to BPN or other opioids or excipients of CAM2038.
- 14. Intolerance to venipuncture and/or difficulty with venous access, as per the judgment of the Investigator/research staff.
- 15. Subject is currently using an investigational drug or monoamine oxidase inhibitor (MAOI) or has used such within the last 30 days (or 5-times the half-life of the drug, if known and longer) prior to first drug administration in the Qualification Phase (i.e., IR morphine sulfate).
- 16. Requires current use of agents that are strong inhibitors or inducers of cytochrome P450 3A4 (CYP 3A4), such as some azole antifungals (e.g., ketoconazole), macrolide antibiotics (e.g., clarithromycin), or protease inhibitors (e.g., ritonavir, indinavir, and saquinavir).
- 17. If the subject is currently on probation or has any pending legal action that could prohibit participation or compliance in the study.
- 18. A subject who, in the opinion of the Investigator, is considered unsuitable or unlikely to comply with the study protocol for any reason.

# 8.3. Qualification Criteria

In addition to the inclusion and exclusion criteria, subjects must meet each one of the following criteria in order to be eligible for participation in the Treatment Phase:

- Maximum effect (Emax) in response to IM hydromorphone 6 mg greater than that of placebo on Drug Liking bipolar VAS (response to hydromorphone 6 mg should be greater than 55 mm in the VAS and a difference of at least 15 mm between placebo and 6 mg) and acceptable overall responses to hydromorphone and placebo on the subjective measures, as judged by the Investigator or designee.
- Emax in response to IM hydromorphone 18 mg greater than that of placebo on Drug Liking bipolar VAS (greater than 60 mm and a difference of at least 20 mm between placebo and 18 mg) and Emax score of at least 20 points, and acceptable overall responses to hydromorphone and placebo on the subjective measures, as judged by the Investigator or designee.
- Acceptable placebo response based on Drug Liking bipolar VAS (score between 40 and 60 mm, inclusive).
- Subject is able to tolerate IM hydromorphone 6 mg and 18 mg, as judged by the Investigator, including ability to complete most pharmacodynamic assessments administered within 5 hours post-dose.
- General behavior suggests that the subject could successfully complete the study, as judged by the research site staff.

Version: 2.0, 17NOV2015 Page 46 of 99

# 8.4. Removal of Subjects from Therapy or Assessment

A subject is free to withdraw his/her consent and discontinue participation in the study at any time for any reason. A subject's participation must therefore be terminated immediately upon his/her request, and the reason(s) for discontinuation appropriately documented.

A subject must be discontinued from the study for any of the following reasons:

- Safety reasons, including AEs or significant concomitant illness, injury, or urgent surgeries/procedures that would, in the judgment of the Investigator, affect assessments of clinical status to a significant extent, require discontinuation of study drug, or both
- At the request of the Sponsor, regulatory agency, or Institutional Review Board (IRB)
- Subject is lost to follow-up
- Subject treatment allocation is unblinded during the Treatment Phase (i.e., individual code break; Section 9.6)
- Death of subject

A subject may also be discontinued from the study, at the discretion of the Investigator and/or Sponsor, for any of the following reasons:

- Subject refuses or is unable to adhere to the study protocol
- Protocol violation
- Pregnancy
- Requirement for continual use of opioid analgesics >7 days or requirement for general anesthesia for surgery

The Investigator must maintain a record of all subjects who discontinue from the study prior to completion; the reason(s) for study discontinuation will be documented. In the event that a subject chooses to withdraw from the study, the Investigator should make a reasonable attempt to obtain and record the reason(s) for withdrawal, if possible, although the subject is not obligated to provide such a reason.

All efforts should be made by the Investigator to continue collection of safety assessments at the protocol-defined intervals, including concomitant medications and AEs in subjects that discontinue study drugs, unless the subject withdraws his/her consent at the time of early discontinuation. The Investigator should also ask the subject to complete Follow-up phone-call, provided that the subject has not withdrawn consent. If a subject refuses to complete Early Termination procedures and/or Follow-up, this information will be recorded.

# 8.5. Study Restrictions

In addition to the inclusion/exclusion criteria described in Sections 8.1 and 8.2, the subject must agree to abide by the following study restrictions:

Version: 2.0, 17NOV2015 Page 47 of 99

- Subjects will be required to abstain from alcohol for 24 hours prior to Screening and before check in to the CRU. Alcohol abstinence will be confirmed with a breath alcohol test.
- Subjects will be asked to abstain from recreational drug use throughout the study, from check-in to the CRU until after discharge following the last hydromorphone administration in the Treatment Phase.
- Subjects will not be permitted to consume caffeine-containing beverages on Hydromorphone Challenge Session days.
- Subjects will be asked to abstain from the following foods from 1 week prior to first drug administration in the Treatment Phase until after study discharge: grapefruit or grapefruit-containing products, pomegranate, pomelo, and star fruit juice/products, as well as foods containing poppy seeds,
- On Hydromorphone Challenge Session days, subjects will be required to abstain from smoking for at least 30 minutes prior to hydromorphone dosing. At other times, smoking will be permitted at short breaks (approximately 5-10 minutes in duration) at the discretion of the CRU staff. If a smoking break is permitted, it must not interfere with study procedures. Subjects will be permitted to use a nicotine-containing transdermal system as needed, at the discretion of the Investigator.
- Subjects will be required to abstain from blood donation for 30 days following the Follow-up visit.
- Subjects will be required to follow the informed consent form (ICF) and any clinic rules and requirements.
- Male subjects should refrain from donating sperm for 3 months after the subjects follow up visit.

Version: 2.0, 17NOV2015 Page 48 of 99

#### 9. TREATMENTS

#### 9.1. Treatment Administration

Subjects will be given a short-acting oral opioid, IR morphine 30 mg, QID, for a minimum of 3 days and a maximum of 7 days prior to the Qualification/Baseline Hydromorphone Challenge Session. One additional dose of IR morphine 30 mg may be administered for the first 3 days of stabilization, as needed, at the investigator's discretion. Subjects will not receive IR morphine 30 mg on the evening and morning prior to hydromorphone dosing in the Qualification/Baseline Hydromorphone Challenge Session (Day -3, Day -2, Day -1) and the evening prior to and morning of CAM2038 q1w dosing (Day 0).

Subjects will receive one of the following weekly doses of CAM2038 q1w (BPN FluidCrystal® Injection depot for once weekly administration), 24 mg or 32 mg (BPN base), on two separate days in the study (Day 0 and Day 7). CAM2038 q1w will be administered by SC injection in the subject's buttocks while rotating between right and left buttocks (0.48 mL or 0.64 mL, respectively).

Hydromorphone (10 mg/mL) will be administered in a randomized manner (placebo, 6 mg and 18 mg) once daily during each 3-day Hydromorphone Challenge Session. Hydromorphone will be administered by 1.8 mL IM injection (described below).

